1. INTRODUCTION

1.1 Background and Rationale

Severe acute malnutrition (SAM) affects nearly 19 million children under the age of 5 annually.¹ Current World Health Organization (WHO) guidelines for treatment of SAM include outpatient treatment with ready-to-use therapeutic food (RUTF). Children with SAM often bear a large burden of infectious disease, have 9 times the risk of all-cause mortality compared to their well-nourished peers, and face a stronger risk of infectious mortality.^{2,3} Because malnutrition can suppress the immune system, children with SAM and co-existing infection are often asymptomatic. As a result, the WHO has recommended that the routine treatment of children with SAM include a broad-spectrum antibiotic. However, the evidence base for this recommendation is minimal. Two studies of amoxicillin as adjunctive therapy for SAM found mixed results.^{4,5} In Malawi, routine amoxicillin led to increased nutritional recovery and decreased mortality.⁴ In Niger, there was no effect of routine amoxicillin on either nutritional recovery or mortality.⁵ Importantly, a majority of the children included in the Malawi study had kwashiorkor, whereas children with kwashiorkor were excluded in Niger. A pooled analysis of the two studies found no benefit of amoxicillin for recovery.⁶ A third study of daily co-trimoxazole for complicated SAM additionally found no benefit for nutritional recovery or mortality.⁷ The role of antibiotics for mortality and nutritional recovery among children with uncomplicated severe acute malnutrition remains unclear.

A recent cluster-randomized trial demonstrated that mass azithromycin distribution reduces all-cause mortality at the community level.⁸ In Niger, Tanzania, and Malawi, mortality was reduced by nearly 14% in communities randomized to biannual mass single-dose azithromycin distribution to children 1-59 months in the MORDOR trial (*Macrolides Oraux pour Réduire les Décès avec un Oeil sur la Résistance*). The largest effects were seen in Niger, with nearly 1 in 5 deaths averted, and in children less than 6 months of age, with approximately 25% reduction in mortality.

Azithromycin as adjunctive therapy may offer several advantages over amoxicillin or co-trimoxazole. First, a single dose of azithromycin has a long half-life, and thus dosing could occur during outpatient follow-up visits and would not rely on caregiver dosing. Second, amoxicillin and co-trimoxazole are much more commonly used for routine treatment in many regions of sub-Saharan Africa than macrolides, and baseline resistance to these antibiotic classes tend to be much higher.⁹ Adjunctive therapy with azithromycin may be preferable, given overall reduced exposure compared to other classes.¹⁰ Third, evidence from the MORDOR study in Niger indicated a substantial reduction in mortality with the use of a single dose of azithromycin in children without established infection. Given that children with uncomplicated SAM by definition do not have an established infection, the rationale for antibiotic use may be similar for that among children in the general population who are receiving presumptive treatment. As children with malnutrition are at particularly high risk of mortality, this subgroup of the population may stand to see greater benefits from a similar antibiotic regimen that has been shown to be efficacious in the general population.

1.2 Design Overview

We propose a randomized controlled trial to examine the effect of the adjunctive administration of azithromycin compared to amoxicillin in the treatment of children aged 6-59 months with uncomplicated SAM. We will randomize children presenting to nutritional programs in Gombe State, Nigeria to a single dose of oral azithromycin or a short course of oral amoxicillin upon admission into the program and follow them at each weekly clinic follow-up visit up to 8 weeks following admission. All enrolled children will receive non-antibiotic routine care for uncomplicated SAM as stated by the Nigeria guidelines, which includes ready-to-use therapeutic food (RUTF). Anthropometric and vital status data will be collected during follow-up. Weight gain and nutritional recovery over the 8-week study period will be compared by study arm.

1.3 Objectives

SPECIFIC AIM 1: Determine the effect of azithromycin on weight gain among children with uncomplicated SAM. *We hypothesize that children randomized to receive azithromycin will experience greater weight gain over an 8-week period compared to those receiving amoxicillin.*

SPECIFIC AIM 2: Determine the effect of azithromycin on nutritional recovery in children with uncomplicated SAM. *We hypothesize that children randomized to receive azithromycin will have increased nutritional recovery 8 weeks after admission to the nutritional program compared to children receiving amoxicillin.*

2. STUDY DESIGN

This randomized controlled trial is designed to determine the effect of administration of azithromycin compared to amoxicillin as part of the treatment of uncomplicated SAM in children aged 6-59 months on weight gain and nutritional recovery. We will randomize children presenting to Taimaka-run nutritional programs at health centers in Gombe State, Nigeria to a single dose of oral azithromycin or a short course of oral amoxicillin upon admission into the program. Apart from the administration of antibiotics, all children will receive standard outpatient treatment for uncomplicated SAM as specified in the guidelines of the government of Nigeria, which includes therapeutic feeding with RUTF. Enrolled children will be followed weekly at each routine clinic follow-up visit up until nutritional recovery. All enrolled children will return for a final study visit at 8 weeks following enrollment. Anthropometric and vital status data will be collected at each follow-up visit. Weight gain and nutritional recovery over the 8-week study period will be compared by arm as a primary outcome and at 12 weeks as a secondary outcome.

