2.5 Outcomes

Primary Outcome

Weight gain over 8 weeks (Specific Aim 1). Weight will be measured at all follow-up time points and weight gain will be defined as grams per kilogram per day (g/kg/day).

Secondary Outcomes

Nutritional recovery by 8 weeks (Specific Aim 2). Nutritional recovery will be defined as a child having WHZ \geq -2 on two consecutive visits and no acute complication or edema for the past 7

[figure not shown]
days AND / OR MUAC of $\geq 125\text{mm}$ on 2 consecutive visits and no acute complication or edema for the past 7 days. The criteria chosen to define the recovery will be the same one we used to admit the child into the program as defined in the national guidelines:

Criteria of admission	Criteria of discharge
MUAC < 11.5cm	MUAC > 12.5cm (for 2 consecutive weeks) Sustained weight gain Clinically well
Bilateral oedema	MUAC > 12.5cm No oedema for 2 consecutive visits Clinically well
WHZ < -3 SD	MUAC > 12.5cm AND WHZ >-2 for 2 consecutive visits Clinically well

- **Weight gain over 12 weeks.** Weight will be measured at all follow-up time points and at 12 weeks after admission to the program. Weight gain will be defined as grams per kilogram per day (g/kg/day).
- **Time to recovery.** Time from enrollment to nutritional recovery (defined above) will be calculated in days by subtracting the date of enrollment from the date of nutritional recovery.
- **Nonresponse at 8 weeks.** Nonresponse will be documented if a child does not meet the criteria for nutritional recovery at 8 weeks.
- **Transfer to inpatient care.** The occurrence, date, and reason for transfer from outpatient to inpatient treatment will be recorded.
- **Mortality by 8 weeks.** Vital status will be assessed at all follow-up time points and mortality will be defined as death during the study period. Date of death will be recorded.
- **Mortality by 12 weeks.** Vital status will be assessed at all follow-up time points and mortality will be defined as death during the study period. Date of death will be recorded.
- **Clinical signs of infection.** At all follow-up time points, clinical signs of infection will be recorded, including care-giver reported experience of fever, diarrhea, vomiting, and respiratory infection/cough and clinical diagnoses made at by site personnel
- **Adverse events.** Adverse events will be reported at all follow-up time points
- **HAZ.** Height or length will be measured monthly and height-for-age z-scores will be calculated.

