3.2 Anthropometry

Anthropometric assessments (height or length, weight, and MUAC) will be recorded by health agents at baseline, weekly until recovery, week 8 and week 12.

Supplies

- Mobile data collection device & accessories
- Height and length tapes
- Digital scale
- MUAC strips
- Chucks and alcohol swabs
- Pens and sharpie markers
- Trash bags
- Extra set of AA batteries (6)

[figure not shown]
Anthropometry Team

Two health agents will conduct anthropometry: 1) examiner and 2) recorder. The examiner will conduct the anthropometric assessments, and the recorder will enter data into the mobile application.

Measuring Length (National operational guidelines for CMAM Nigeria)

How to measure LENGTH (when lying down) If the child is less than 87cm, he/she should be measured lying down.

1. One person holds the child's head, making sure the child's head is touching the back of the board. The child's eyes should be looking straight up.
2. The other person holds down the child's knees, pressing the sliding wood piece against the child's heels and soles of the feet.
3. Align the child with the board
4. Child's arms should be lying alongside his/her body, and if necessary, the mother can hold the arms down
5. The person holding the feet reads the measurement.

[figure not shown]

Measuring Height (National operational guidelines for CMAM Nigeria)

How to measure HEIGHT (when standing) If the child is more than 87cm, he/she should be measured standing.

1. Place the child's feet flat and together in the centre of and against the back and base of the wall.

2. One person places their right hand just above the child's ankles on the shins, left hand on the child's knees and push against the wall. Make sure the child's legs are straight and the heels and calves are against the wall
3. Tell the child to look straight ahead making sure the child's line of sight is level with the ground.
4. The second person should place their open left hand under the child's chin. Do not cover the child's mouth or ears. Make sure the shoulders are level, the hands are at the child's side, and the head, shoulder blades, and buttocks are against the wall.
5. When the child's position is correct, person holding the legs reads (at eye level) and call out the measurement to the nearest 0.1 cm.

Measuring Weight

Tempered glass digital standing scales will be used to weigh infants and children to the nearest 0.1 kg.

For infants and children who cannot stand:

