5. ADVERSE EVENTS

5.1 Adverse Event Monitoring and Reporting

Parents or guardians of enrolled children will be instructed to report any adverse events experienced within the 7 days following the enrollment visit, by phone or in person. At all follow-up visits, study staff will inquire about the child's experience of adverse events, including if the child had any of the following symptoms:

- Fever
- Diarrhea
- Vomiting
- Abdominal pain
- Skin rash
- Constipation

The study team will assess whether the parent or guardian sought care for the child since the last visit and if so, what the reason was for the health care visit and if the child was hospitalized.

Serious adverse events will be defined as death, hospitalization, or any other life-threatening situation. Serious adverse events will be reported to the Medical Monitor within 24 hours.

The health agent conducting the follow-up visit will email the Taimaka investigators if a serious adverse event is diagnosed, the Taimaka investigators will immediately email the Medical Monitor and the UCSF study team. The Medical Monitor will make a determination as to whether the event could be reasonably considered to be related to the study drug and will report the results of this determination to the study investigators, who will report to the UCSF IRB and the DSMC as needed. Information on all adverse events, serious and non-serious, will be recorded on data collection forms through the mobile application.

See Appendix 5 for more information on SAE reporting.

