6. DATA COLLECTION, MANAGEMENT, AND SECURITY

6.1 Data Collection

Data will be collected on enrolled children at baseline (time of enrollment), and follow-up weeks 1-12. Written informed consent will be collected on paper and the study officer administering treatment will record treatment administration on Taimaka's internal ap. All other data will also be collected electronically on mobile devices using ODK mobile application.

Data from the study participants is stored in the same database as data from all of Taimaka's patients. Taimaka will share the entire database with UCSF, and the UCSF study team will write a carefully-worded statistical programming script to only select records and data of the study participants.

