9.2 Statistical Analysis

Baseline characteristics. Characteristics of the study population collected at baseline will be summarized using frequencies and percentages for categorical variables and means and standard deviations or medians and inter-quartile ranges for continuous variables. Baseline characteristics will be compared by treatment arm using Fisher's exact test for categorical variables and t-tests or Wilcoxon rank-sum tests for continuous variables.

Specific Aim 1. The primary analysis will compare weight gain velocity (g/kg/day) between groups over the 8-week follow-up period. We will estimate mean differences and 95% confidence intervals for the difference using a linear regression model with an indicator for study group.

$$E[Y | X = x] = \beta_0 + \beta_1 X + e$$

Where:

- **Y = weight gain velocity from enrollment to 8 weeks**
- X = binary indicator for treatment group ($X=1$ for azithromycin, $X=0$ for a short course of oral amoxicillin)

- β_1 = difference in weight gain velocity between the azithromycin group compared to a short course of oral amoxicillin group
- $e \sim N(0, \sigma^2)$

Sensitivity analyses will include similar linear models to assess period-specific weight gain by group from week 0-1, 1-2, 2-4, and 4-8.

Specific Aim 2. The primary analysis will compare nutritional recovery by 8 weeks from baseline by arm. We will use log-binomial regression for this analysis to estimate the risk ratio. We will use the following model:

$$\log[P(Y = 1|X_1 = x_1)] = \beta_0 + \beta_1 X_1 + e$$

Where:

- **Y = binary indicator for nutritional recovery by 8 weeks ($Y=1$ for recovered, $Y=0$ for not recovered)**
- X = binary indicator for treatment arm ($X=1$ for azithromycin, $X=0$ for a short course of oral amoxicillin)
- e^{β_1} = relative risk of nutritional recovery in azithromycin arm compared to a short course of oral amoxicillin arm
- $e \sim N(0, \sigma^2)$

If the log-binomial model fails to converge, we will use a modified Poisson model with robust standard errors as an alternative.

Secondary outcomes.

Time to event outcomes (time to recovery and time to mortality) will be assessed visually using Kaplan-Meier curves and compared by arm using the log-rank test.

Binary outcomes will be analyzed using modified Poisson regression for rare outcomes (e.g. mortality) or log-binomial regression for common outcomes (e.g. malaria), using models similar to the one described above for Specific Aim 2.

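### If weekly visits stop at recovery, later symptoms and infection signs can be asked about less often in the faster-recovering arm, which can modestly favour that arm

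*Combined protocol and SAP*

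**What the plan says.** **Schedule.** Section 2 states "Enrolled children will be followed weekly at each routine clinic follow-up visit up until nutritional recovery", then "All enrolled children will return for a final study visit at 8 weeks following enrollment". Section 3.2 gives the same pattern for anthropometry: "weekly until recovery, week 8 and week 12". Two other places mention no stop at recovery. Section 1.2 will "follow them at each weekly clinic follow-up visit up to 8 weeks following admission", and Section 6.1 says "Data will be collected on enrolled children at baseline (time of enrollment), and follow-up weeks 1-12".

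**Collection.** Section 5.1: "At all follow-up visits, study staff will inquire about the child's experience of adverse events". Section 2.5: "At all follow-up time points, clinical signs of infection will be recorded", and it lists adverse events on the same footing. Section 3.7 ties clinical examination findings to enrollment, the weekly visits and week 8. Section 5.1 asks about care-seeking and hospitalization since the previous visit, but gives no recall period for symptoms. Caregivers are also told to report events in the first 7 days.

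**Analysis.** Section 9.2: "Binary outcomes will be analyzed using modified Poisson regression for rare outcomes", with log-binomial regression for common ones. No offset, common window or per-visit rate is given.

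**Expected recovery.** Section 1.3 hypothesizes more recovery with azithromycin. Section 9.1 plans on 36% with amoxicillin and a 12-point difference.

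**The concern.** On the schedule in Sections 2 and 3.2, a recovered child is not asked about symptoms between recovery and week 8, while an unrecovered child is asked every week. The number of inquiries is set after randomization by an outcome the trial hopes to shift, so randomization does not balance it. If azithromycin speeds recovery, its children have fewer chances to report fever, diarrhea, vomiting or cough. A lower proportion ever reporting could then be read as a tolerability or infection benefit when it partly reflects fewer questions. Adverse events and clinical signs of infection are both listed secondary outcomes.

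**Working it through.** **Inputs from the documents.** Recovery of 36% with amoxicillin and 36 + 12 = 48% with azithromycin; 600 children less 10% loss = 540, so 270 per arm; two-sided 5% test (Section 9.1). Recovery needs two consecutive qualifying visits (Section 2.5), so the earliest recovery visit is taken as week 2.

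**Assumptions not in the documents.** The timing of recovery; the same report probability *q* per inquiry in both arms, 5% to 20%; independence between visits; each inquiry catches only the week before it; the same risk after recovery.

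**Step 1. Reproduce the plan's figure.** SE under the null = √(2 × 0.42 × 0.58 / 270) = 0.0425. SE under the alternative = √((0.36 × 0.64 + 0.48 × 0.52) / 270) = 0.0422. (0.12 − 1.96 × 0.0425) / 0.0422 = 0.87, so power is 80.8%, against 80% stated. The 36% vs 48% contrast is therefore the plan's own.

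**Step 2. Inquiries per child over 8 weeks.** A child recovering at week *r* < 8 has *r* weekly visits plus week 8, so *r* + 1; all others have 8. With recoveries spread evenly over weeks 2-8, a recovered child averages (3+4+5+6+7+8+8)/7 = 5.86.

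- Azithromycin: 0.48 × 5.86 + 0.52 × 8 = 6.97
- Amoxicillin: 0.36 × 5.86 + 0.64 × 8 = 7.23
- Ratio: 0.964

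**Step 3. Probability of ever reporting.** P = 1 − mean of (1 − *q*)^visits. At *q* = 0.10 the mean of 0.9^visits is 0.5495 among recovered children and 0.9^8 = 0.4305 among the rest.

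- Azithromycin: 1 − (0.48 × 0.5495 + 0.52 × 0.4305) = 0.512
- Amoxicillin: 1 − (0.36 × 0.5495 + 0.64 × 0.4305) = 0.527
- Null risk ratio: 0.973

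**Step 4. Range.** Rejection rate is from the two-proportion z-test, 270 per arm, with no true effect.

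| Recovery timing (assumed) | Inquiry ratio | Null risk ratio, *q* 5% to 20% | Rejection rate |
|---|---|---|---|
| Even over weeks 6-8 | 0.995 | 0.996 to 0.998 | 5.0% |
| Even over weeks 2-8 | 0.964 | 0.969 to 0.981 | 5.7% to 7.1% |
| Even over weeks 3-6 | 0.958 | 0.964 to 0.979 | 5.9% to 7.3% |
| All at week 3 | 0.927 | 0.936 to 0.961 | 7.6% to 11.8% |

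The arithmetic limit is every recovery at week 2: inquiry ratio 0.903, null risk ratio 0.913 to 0.942, rejection 9.5% to 17.9%.

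**Step 5. When the bias vanishes.** With equal recovery timing, visit counts match. With complete week 8 recall back to the last visit, all 8 weeks are covered in both arms: 1 − 0.95^8 = 33.7% at *q* = 0.05 and 1 − 0.90^8 = 57.0% at *q* = 0.10, so the risk ratio is 1.00.

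**Step 6. Common window.** Counting only weeks 1, 2 and 8 gives three inquiries per child: 1 − 0.95^3 = 14.3% and 1 − 0.90^3 = 27.1%, the same in both arms.

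**Step 7. Dividing by visits.** If week 8 recall does cover the gap, events are equal but azithromycin has fewer visits. The per-visit rate ratio is then 1/0.964 = 1.04 with recoveries over weeks 2-8, and 1/0.927 = 1.08 with all at week 3. This bias runs the other way.

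**The case against.** A reader might infer that the faster-recovering arm will look safer overall. The documents do not support that.

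- **The schedule is contradictory.** On Sections 1.2 and 6.1 as written, inquiry continues for everyone and there is no difference. This stands: the point is conditional on Sections 2 and 3.2, which are the places that say what happens at recovery.
- **Week 8 recall may fill the gap.** All children return at week 8, and the study forms (Appendix 2) are not visible here. This stands as a possibility, but the text applies recall since the last visit only to care-seeking and hospitalization.
- **Ever/never is an inference.** The binary examples in Section 9.2 are mortality and malaria, and no analysis variable is defined for adverse events or infection signs. This stands, and is a further reason to define one.
- **The direction is not certain.** Section 5.2 refers poorly responding children to inpatient care. If weekly inquiry ends there, which is not stated, the slower arm also loses inquiries and the bias could be offset.
- **The gravest and earliest events are largely protected.** Vital status is recorded up to week 12 (Section 3.6), hospitalization is asked since the last visit, and the 7-day reporting window and week 1 visit come before recovery can be declared.
- **Twelve percent is a corner case.** It needs nearly all recoveries by about week 3 and a 20% report rate, which sits poorly with 64% of amoxicillin children unrecovered at week 8.

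What remains is that later symptoms and infection signs depend on an outcome for their ascertainment, and the written plan does not secure equal inquiry.

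**Conclusion.** The concern holds in a limited form. If weekly inquiry stops at recovery, a per-child ever/never comparison of later symptoms and infection signs can modestly favour the faster-recovering arm under no true difference. At the planned 36% vs 48% recovery the null risk ratio is about 0.96-0.98 and the 5% test runs at about 6%-7% with recoveries spread over weeks 2-8 or 3-6. It is close to nil if recoveries are late and about 12% only in the early corner case. These sizes rest on the assumed timing, report rate and one-week capture, and need both a real recovery difference and incomplete week 8 recall. This is worth correcting because correction is cheap; it does not threaten the primary result.

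**What to change.** 1. Reconcile Sections 2 and 3.2 with Sections 1.2 and 6.1 on whether weekly symptom inquiry continues after recovery. If it continues for all children, saying so settles the matter.
2. If it stops, define the analysis variable for adverse events and infection signs, and make the main comparison cover the visits scheduled for every child: weeks 1, 2 and 8. Use one fixed recall period for the week 8 symptom question, identical for recovered and unrecovered children.
3. Report events over the full 8 weeks per child-week covered by inquiry, with robust standard errors, as supportive only. That denominator is determined after randomization, and a log-visits offset can bias against the faster-recovering arm if week 8 recall covers the gap.

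The cost is protocol and SAP wording plus one line on the week 8 form, with no added visits or sample size. The downside is that the common window leaves out some mid-period events; the supportive analysis keeps those that were captured.
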